Prior to enrollment patients will be on a stable dialysis regimen. This could be only haemodialysis (HD), only peritoneal dialysis (PD) or combined HD and PD. The choice of dialysis regimen will be decided upon by the investigator and individualised to remove adequate oxalate to minimise the risk for systemic oxalosis. The PD regimen (number of days/week, hours per treatment, volume of dialysis buffer) and HD regimen (number of days/week; hours per treatment; blood and dialysate flow rates; and HD membrane) will be maintained for the duration of the study. This will be monitored and recorded by measuring volume of spent dialysate from HD and PD and quantifying dialysis dose of each HD session in terms of Kt/V measurement using an online clearance monitor. Each patient's dry weight (target bodyweight after the dialysis session) will also be recorded.

The total plasma oxalate (the primary end point of this study) will be measured at weeks 2, 4, 6, 8, 10, 12, 14, thereafter monthly for the first 24 months of continued treatment and every third or fourth month during the last 12 months of the continued treatment period (Figure 6 and Figure 7). A blood sample will be obtained after two consecutive days of completed dialysis regimen the preceding days, but prior to the dialysis session on the day of sampling. The plasma samples will be processed at each clinical site and analysed for total plasma oxalate at the Academic Medical Center, Amsterdam and for free plasma oxalate at the local lab (Bonn University Clinical laboratory).

Speckle Tracking Echocardiography and traditional echocardiography will be performed, if possible, at screening visit (+/- 1 month) or before start of continued treatment period (at visit week 14). Speckle Tracking Echocardiography and traditional echocardiography will then be repeated at week 24 in the continued treatment period and thereafter every 6 months until end of treatment, if possible.

Figure 6: Study design for OC5-OL-01 - the first 14 weeks of the study.

	Screening (0-4 weeks)		Baseline (4 weeks)		Treatment (6 weeks)						Post-trtm (4 weeks)				
Week	0	1	2	3	4	5	6	7	8	9	10	11	12	13	14 ²
Clinic visit	X	X	X	X	X	X	X	X	X	X	X	X	X	X	X
Plasma oxalate	X		X	X	X	X	X	X	X	X	X	X	X	X	X
Stool	X	X	X	X	X	X	X	X	X	X	X	X	X	X	X
Safety labs	X	X	X	X	X	X	X	X	X	X	X	X	X	X	X
STE	X ²	:				:					:				

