6.2.3 Treatment period – the first 6-week treatment period (study week 5-10)

During the initial 6 weeks treatment period, the patient will be followed by clinic visits at week 6, 8 and 10, according to Table 4: Schedule of assessments – the first 14 weeks of the study.

At the clinic visits, a blood sample for plasma oxalate will be taken prior to the dialysis session.

At week 10, faecal sample will be taken as well as safety labs.

At each clinic visit the patient will be assessed for the presence or absence of Adverse Events and changes in concomitant medications.

The patient will receive shipments of study drug bi-weekly at week 4, 6 and 8. Remaining study drug will be returned to the clinic or site pharmacy at clinical visits weeks 6, 8, 10 and 12.

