6.2.4 Post treatment period – 4 weeks without study drug (study week 11-14)

During the post-treatment period study visits will take place at week 12 and 14. A blood sample will be taken for determination of plasma oxalate prior to the dialysis session in week 12 and 14.

At week 14 faecal sample will be taken as well as safety labs.

At each clinic visit the patient will be assessed for the presence or absence of Adverse Events and changes in concomitant medications. At the clinical visit week 14 a physical examination including vital signs will be performed.

Adverse Drug Reactions (i.e. AEs that are possibly or probably related to study treatment, see section 11.1), which are unresolved at the time of week 14 clinic visit, should be followed until the event has resolved or, if persistent, has been assessed as “chronic” or “stable” for patients not participating in the continued treatment period.

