12 STATISTICS

12.1 Statistical methods

Efficacy: The primary endpoint, change in total plasma oxalate from baseline, will be evaluated over time for each patient. Evidence for efficacy will be provided as the combined evaluation of individual case studies. Plasma oxalate levels will be measured on a monthly basis throughout the first 24 months of the continued treatment period and once every 3-4 months during the last 12 months of the continued treatment period. All secondary endpoints will be analysed using the same methodology.

For the primary endpoint the change in total plasma oxalate levels will be based on the average from two baseline measurements (week 2 and week 4) and one measurement every 4th week throughout the first 24 months of the continued treatment period and every 3-4 months during the last 12 months of the continued treatment period.

The change in plasma oxalate during 4 weeks follow-up period after the end of the 6 weeks treatment period with OC5, will be based on one measurement at week 10 and one measurement at week 14. The last observation will be carried forward in case of missing values at week 14 and/or week 10.

Two interim analyses will be performed: The first analysis will be based on patients who complete the first year of continued treatment. The second interim analysis will be based on all study data obtained up to 24 months. Both interim analyses will evaluate all captured efficacy and safety parameters.

The individual changes in plasma oxalate per week will also be calculated as an average slope using regression of plasma oxalate by week.

The study involves a small number of patients and natural history data on changes in total and free plasma oxalate for this population is limited. Response to treatment is likely to vary depending on the baseline plasma oxalate level, individual hepatic oxalate production and age of each patient. Accordingly, the sample size is not based on assumptions of efficacy outcome and statistical power, and the definition of analysis populations is not applicable. Any inferences from the data will be based on clinical relevance rather than statistical significance.

Safety: The safety will be summarised using descriptive statistics based on frequency, seriousness and severity of treatment emergent AEs. Clinically relevant changes in safety laboratory parameters will also be summarised.

All statistical analyses will be further defined in a Statistical Analysis Plan.

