2 STUDY INFORMATION

2.1 Study Objective(s)

The primary objective of this study is to evaluate the efficacy of OC5 to reduce total plasma oxalate levels during OC5 treatment in patients with Primary Hyperoxaluria (PH) who are on dialysis.

The secondary objectives of this study are:

- To evaluate the efficacy of OC5 to reduce free plasma oxalate levels during OC5 treatment in patients with Primary Hyperoxaluria (PH) who are on dialysis.
- To evaluate the safety of OC5 in patients with PH who are on dialysis.
- To evaluate changes in number of *O. formigenes* in faeces following administration of OC5.
- To evaluate effect of stopping OC5 treatment for 4 weeks after the first 6 weeks of treatment.
- To evaluate results from Speckle Tracking Echocardiography and traditional echocardiography.

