6 STATISTICAL ANALYSIS

6.1 General considerations

All evaluations will be explorative in nature, unless stated otherwise. There will be no formal statistical significance testing.

Raw data (in listings) will be presented in the same precision as received. Appropriate rounding will be performed for the summary statistics: arithmetic mean, median, SD (standard deviation) and two-sided 95% confidence limits will be presented with one more decimal than the original data; minimum and maximum values will be presented with the same precision as the original data. In special cases, e.g. after conversion of data, the number of decimals will be determined based on relevance. In frequency tables, percentages will be presented with 1 decimal unless otherwise stated. P-values will be presented with 3 decimals, and those smaller than 0.001 will be replaced by <0.001.

Descriptive statistics presented in summary tables for continuous variables will be the number of non-missing observations (n), arithmetic mean, SD, SE, median, Q1 and Q3, minimum and maximum. All plots will be created using scheduled protocol time or visit on the x-axis. Mean plots will be presenting mean +/- SE. For qualitative data, frequency counts and percentages will be determined. The denominator used when calculating percentages will be the number of subjects in the applicable analysis population.

Baseline is generally defined as the last non-missing and valid measurement/assessment before first dose of study drug. Unscheduled measurements are excluded as baseline value, unless otherwise specified. Change from baseline is calculated as the value at a specific time point minus the value at baseline. For this study, the following definitions are used to define the baseline measurement:

Vital signs: The screening value is used as baseline.

Plasma oxalate: The primary baseline is defined as an average of the available baseline measurements at weeks 2 and 4 (i.e. Visits 2 and 3 respectively). If one baseline measurement is missing for plasma oxalate, the remaining value will be used as baseline value. An additional baseline is the week 10 (Visit 6) assessment of plasma oxalate levels which will serve (only) as a baseline for the assessment of the change in plasma oxalate levels following the 4 week off-treatment period (secondary endpoint). For analyses in the CT phase of the study, a third baseline is defined, being the week 14 value at week 14 of the initial TRT phase.

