 - If start day is missing, it will be set to the first day of the start month.
 - If both start day and month are missing, then day and month are imputed with the first month and the first day of that month of the available year.
- If end date is completely missing and ongoing is not applicable, then end year is study treatment year-1, end month is the same as the month of the reference date (i.e. the first dose date), and end day is day+1 of that month.
- If the end year is available and the difference between the year of first treatment and the end year of MH is larger than 1 year, then the following applies:
 - If both end month and end day are missing, then the end date will be imputed as 31 December of the available year.
 - If only end day is missing, then the end date will be imputed as the last day of the available month.
- If the end year is available and the difference between the year of first treatment and the end year of MH is 1 year, then the following applies:
 - If month and day are both missing, then month is set to the month of the reference date (i.e. the first dose date), and end day is set to the day of the reference date+1.
 - If only day is missing and month is the same as the month of the reference date, (i.e. the first dose date), then end day is set to day+1 of that month.
 - If only day is missing and month is different from the month of the reference date, (i.e. the first dose date), then end day is set to the last day of the available month.
- If the difference between the year of first treatment and the end year of MH is 0, then the following applies:
 - If both end day and month are missing, then month is imputed with the month of the reference date (i.e. first dosing date) and the end day is set to day-1 of that month, unless the day of the reference is the first day of the month, in which case end day will be set to the same day.
 - If only end day is missing, then the day will be set to the last day of the available month.

For untreated patients, it is not possible to determine MH in the year prior, as there is no reference date (i.e. first dosing date) available.

Plasma Oxalate during 4 -week treatment-off period

In case of missing values for week 10, 12 or 14, the method of LOCF will be applied to calculate CFB values.

Other

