6.6.2 Secondary endpoint

All secondary endpoint analyses will be performed for the FAS only, unless specifically stated that mFAS will also be used. All secondary endpoint analyses will be done on the overall treatment period, unless otherwise specified.

Free plasma oxalate

Change in free plasma oxalate level during OC5 treatment will be analyzed descriptively (tables and plots) as described for the primary endpoint.

Total and free plasma oxalate levels from week 10 to week 14

After 6 weeks of treatment, there is a 4 week off-treatment period scheduled. Change in total and free plasma oxalate levels following the 4 week off-treatment at week 12 and 14 will be calculated as the value at visit 12 or 14 minus the visit value at week 10. Summary statistics of the measurements will be presented on a per-visit basis. Both the actual value as well as the change from baseline value will be presented for the FAS. For handling missing data in summary statistics for CFB values, see section [6.2](#).

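### LOCF for the off-treatment change in plasma oxalate gives zero by construction when both off-drug values are missing, and so shrinks any real effect of stopping OC5

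*SAP*

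**What the plan says.** One secondary objective (SAP 2.1) is this: "To evaluate effect of stopping OC5 treatment for 4 weeks after the first 6 weeks of treatment". The endpoint that serves it, in SAP 6.6.2, is a change that "will be calculated as the value at visit 12 or 14 minus the visit value at week 10". SAP 6.1 sets the reference value: "An additional baseline is the week 10 (Visit 6) assessment of plasma oxalate levels". SAP 6.6.2 applies this to total and free plasma oxalate, in the FAS, which needs only one dose.

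For missing values, SAP 6.2 has a rule specific to this endpoint: "In case of missing values for week 10, 12 or 14, the method of LOCF will be applied to calculate CFB values". Protocol 12.1 has a similar one: "The last observation will be carried forward in case of missing values at week 14 and/or week 10". The SAP adds week 12, which the protocol sentence does not name. Both depart from the general position at the start of SAP 6.2, which is to impute nothing outside listed exceptions and to analyse the data available at each visit. Neither document gives a reason for the exception or an alternative analysis of this endpoint.

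On timing, protocol 6.2.3 places the first treatment period in study weeks 5 to 10, and protocol 6.2.4 places the drug-free period in weeks 11 to 14. Protocol 6.1 has plasma oxalate "measured at weeks 2, 4, 6, 8, 10, 12, 14", so week 12 is the only sample between the last on-drug value and week 14.

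**The concern.** The endpoint contrasts an on-drug value with an off-drug value. LOCF can fill the off-drug side with the on-drug value, and the contrast then disappears through arithmetic rather than through anything that happened to the patient. Because the FAS needs only one dose, a patient who leaves during weeks 5 to 10 can be counted as having no change after stopping without ever being observed off drug.

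At stake is the descriptive mean change on which the objective of stopping OC5 is judged. The study has one arm and no formal testing, so the displayed mean and its spread are the evidence. The shrinkage is not safely conservative either. A small change after stopping can be read as a drug that did nothing or as a drug whose effect persists.

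**Working it through.** **Inputs.** Change = week 12 or 14 minus week 10 (SAP 6.6.2). Carry-forward applies to weeks 10, 12 and 14 (SAP 6.2). Samples are taken every two weeks from week 2 to week 14 (protocol 6.1). Planned N is 6 to 12 (SAP 2.4), and 12 patients received study drug (protocol 11.5.1.2). The documents give no missing-data rate, expected change or SD for this endpoint, so there is no plan figure to reproduce.

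**Step 1: apply the rule to one patient.** Assumed profile in micromol/L, for illustration only: week 8 = 85, week 10 = 80, week 12 = 85, week 14 = 90.

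| Missing | Value carried | Week 12 change | Week 14 change |
|---|---|---|---|
| none | none | 85 - 80 = +5 | 90 - 80 = +10 |
| 12 and 14 | week 10 into both | 80 - 80 = 0 | 80 - 80 = 0 |
| 10, 12 and 14 | week 8 into all | 85 - 85 = 0 | 85 - 85 = 0 |
| 12 only | week 10 into 12 | 80 - 80 = 0 | +10 |
| 14 only | week 12 into 14 | +5 | 85 - 80 = +5 |
| 10 only | week 8 into 10 | 85 - 85 = 0 | 90 - 85 = +5 |

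Rows two and three, and the week 12 entry in row four, are zero whatever values are assumed. The last row is not. Had week 8 been 75, the same pattern would give +10 and +15, too large instead of too small. With only week 10 missing, the substitute is still an on-drug value and the error has no fixed direction.

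**Step 2: effect on the mean, both off-drug values missing.** If k of N patients contribute zero and the rest are observed, then in any data set

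LOCF mean = (1 - k/N) x mean of the observed pairs.

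If missingness is unrelated to the change, the observed-pair mean estimates the true mean change, so the LOCF mean estimates (1 - k/N) times it.

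- N = 12: k = 1, 11/12 = 0.92; k = 2, 10/12 = 0.83; k = 3, 9/12 = 0.75.
- N = 6: k = 1, 5/6 = 0.83; k = 2, 4/6 = 0.67; k = 3, 3/6 = 0.50.

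**Step 3: only week 14 missing.** Let r be the week 12 change divided by the week 14 change, which is unknown. The multiplier is 1 - (k/N)(1 - r). For r from 0.25 to 0.75 at N = 12, it is 0.94 to 0.98 for k = 1 and 0.81 to 0.94 for k = 3.

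**Step 4: SD and SE.** Let the true change have mean m and SD s, with n = N - k observed and p = n/N. The expected variance with k zeros added is p s² + n(1 - p)m²/(N - 1). For N = 12 and k = 3 this is 0.75 s² + 0.2045 m².

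- Assumed m = 10, s = 10: 75 + 20.45 = 95.45, so SD 9.77 and SE 9.77/√12 = 2.82. Observed pairs give SE 10/√9 = 3.33. Simulation with 200,000 replicates gave the same 2.82 and 3.33.
- Assumed m = 20, s = 10: 75 + 81.8 = 156.8, so SD 12.5. The zeros now raise the SD.

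Here the SD falls only if m is below √(11/9) = 1.11 times s. The SE stays below the observed-pair SE up to m of about 1.69 s, because the divisor counts patients who supplied no off-drug value.

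**The case against.** The case for leaving the rule alone is that it will rarely bite and can be seen through. Protocol 7.3 asks early leavers in the first 14 weeks to complete the week 14 assessments. Visits can be combined with dialysis attendance (protocol 4.6.1). Eight of the 12 treated patients went on to continued treatment, which starts after week 14 (protocol 11.5.1.2). LOCF is confined to the change values, while actual values are also tabulated by visit (SAP 6.6.2), and individual plots and listings show each patient's course. The endpoint is secondary, nothing is formally tested, and efficacy is to rest on combined case studies (protocol 12.1).

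This stands as a limit on impact. It does not repair the rule, because the tabulated mean change is still wrong whenever the rule is used. A sample taken at withdrawal is also not a four-week off-drug value. For free oxalate, protocol 10.1 relies on whatever local results were available before Amendment VII, so gaps at particular weeks are plausible there even in patients who continued.

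A reader might infer more than the documents support:

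- That any missing value forces a zero. With only week 14 missing, the carried value is off drug.
- That carrying week 12 captures half the effect. It is half the time; the share of the effect is unknown.
- That the zeros always understate the spread. Step 4 shows that the SD can go either way.
- That observed pairs are unbiased whenever data are missing at random. They need missingness unrelated to the change. Protocol 12.1 expects response to vary with baseline oxalate, so dependence on level could bias them too.

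**Conclusion.** The point holds as an analysis choice worth changing. Following SAP 6.2 as written gives a zero change for a patient with no off-drug value, a zero week 12 change when week 12 alone is missing, and a two-week value labelled as four weeks when week 14 alone is missing. With both off-drug values missing in k of N patients, the mean is 1 - k/N of the observed-pair mean as a matter of algebra. It is that fraction of the true change if missingness is unrelated to the change. At N = 12, each such patient removes one twelfth, about 8%.

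Two conditions govern whether this matters in practice. There must be a real change after stopping, since added zeros do not bias a mean whose true value is zero. And some values must be missing; the documents do not say how many, and the answer may be none. It would therefore go too far to say that the reported result will be biased toward no effect. What can be said is that the rule produces that bias under these conditions, usually with an SE smaller than the observed pairs would give.

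**What to change.** In SAP 6.2, replace the carry-forward rule for this endpoint. The analysis becomes the observed week 10 to 12 change and the observed week 10 to 14 change, each in patients with both values, with n shown on each line. This restores the SAP's own default. If LOCF is kept, show it as a separate line labelled supplementary, with the number of carried values.

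Record the departure from protocol 12.1 in SAP section 7, which also settles the mismatch over week 12. Protocol 12.1 can be corrected at the next amendment. Protocol 19 requires a written amendment with prior ethics committee and authority approval, so an amendment for this alone is hard to justify.

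The cost is a short SAP edit and a small change to tables 14.2.9 and 14.2.18. Patients lacking either value drop out of the line concerned, including those missing only week 10, who would otherwise have had an on-drug week 8 substitute. In a study of about 12 that loss is noticeable. The observed-pair mean also keeps its own condition: it is unbiased only if missingness is unrelated to the change, and the report should say so.

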6.3 Interim analysis

A first interim analysis is planned when 6 of the enrolled patients have been followed for at least the first year of continued treatment (i.e. until week 52). Hence the statistical presentations and interim report of the first interim analysis will be created using the data from the first 6 patients who completed 12 months of continued treatment.

A second interim analysis is planned when all enrolled patients completed 24 months of continued treatment (i.e. until week 104) in the CT study phase, and no report is planned but the data will be used for the ASN (American Society of Nephrology) congress.

Both interim analyses are primarily intended to help understand if OC5 treatment in dialysis patients with PH:

- Stabilizes or reduces plasma oxalate
- Stabilizes or improves cardiac function parameters (assessed through Speckle tracking and traditional echocardiography)

6.4 Subject and study disposition

6.4.1 Inclusion/exclusion criteria

An individual patient listing of the deviations from inclusion and exclusion criteria will be presented. Eligibility information is collected at screening and at week 4 and will therefore be presented per visit in the listings.

It should be noted that the CRF and thus the database for inclusion/exclusion criteria differs between centers. This may lead to separate listings per center.

6.4.2 Screen failures

Data for screening failures including the reasons will be listed as available.

6.4.3 Disposition

An overview summary table will be created, stating the number of patients per site, including site number, location/country and investigator.

In addition, to present disposition, a summary of the number/percentage of patients screened (if available), enrolled, treated/exposed to treatment, completed and withdrawn will be created. In the same summary, the number/percentage of patients in the FAS, the mFAS, enrolled/completed/withdrawn per treatment period (TRT and CT) will be presented. Frequency and percentage for withdrawal reasons as collected in the database will be added as well.

